Objectives	Primary: To characterize the effect of a 12-week exercise rehabilitation program on symptom burden at 12 weeks in adults on hemodialysis (HD) Secondary: To characterize the effect of a 12-week exercise rehabilitation program on: - Symptom burden at 12, 26 and 52 weeks in adults on HD - Generic health related quality of life at 12, 26 and 52 weeks in adults on HD Tertiary: To determine the effect of a 12-week exercise rehabilitation program on: - Self-reported time required for recovery post hemodialysis at 12, 26, and 52 weeks - Physical activity behavior at 12, 26, and 52 weeks - Exercise capacity at 12, 26 and 52 weeks - Frailty status at 12, 26, and 52 weeks - Self-efficacy to exercise at 12, 26, and 52 weeks - Hospitalization rate over 1 year and hospital length of stay - Mortality at 1 year
Duration	4 years
Population	Adults on chronic in-centre hemodialysis for greater than 3 months with at least one hemodialysis-related symptom will be enrolled (n=150).
Design	Single centre randomized controlled trial with 1-to-1 parallel design, allocation concealment and assessor blinding.
Inclusion / Exclusion Criteria	Inclusion Criteria: Participants must be able to understand and provide written informed consent in English; greater than or equal to 18 years old; greater than 3 months after starting chronic HD; no expected change in dialysis modality or relocation outside of Winnipeg during intervention period (12 weeks); assessed to be safe and able to exercise by HD unit nephrologist; Exclusion Criteria: acute coronary syndrome in past 3 months; unstable arrhythmia; shortness of breath at rest or with minimal activity (NYHA Class 4); symptomatic hypoglycemia (> 2x/week in week prior to enrolment); currently participating in the MRP clinical intradialytic cycling program; score of 0 on DSI when administered at time of consent
Study Arms	Intervention arm: Standard care plus a 12 week structured rehabilitation program including lifestyle education, home-based resistance exercise and cycling during HD; n=75 Control arm: Standard care including baseline exercise counseling; n=75
Study Endpoints Primary, Secondary and Mechanistic	Primary outcome: Change in symptom burden over time (12 weeks) as measured by Dialysis Symptom Index (DSI) severity score. Secondary outcomes: Change in generic health-related quality of life over time (12, 26, 52 weeks) as measured by EuroQol 5D-5L and EuroQol visual analogue scale Change in: modified symptom burden (modified DSI severity score); time for recovery post-HD; frailty status (Fried criteria); physical activity level (accelerometer and Godin-Shephard Leisure Time Physical Activity Questionnaire); exercise capacity (Incremental Shuttle Walk Test); self-

	efficacy for exercise (Self-Efficacy for Exercise Questionnaire; hospitalization rate (number hospital days admitted/patient year); all cause 1 year mortality
Brief Summary of Analysis	Sample size : The following assumptions were made: alpha 0.05; power 0.80; 30% dropout and 25% absolute difference in proportion of individuals in whom DSI severity score decreases by 7 points or more (minimal clinically important difference). Therefore, assuming a baseline symptom prevalence of 50% of individuals in each study group, 150 patients (75 in each arm) will be randomized and we will be able to detect a 25% reduction in the primary outcome.
	Primary analysis : Intention-to-treat, available-case basis, in the intervention versus control arm, using Chi-square test and logistic regression for categorical outcomes and t-tests/MannWhitney U for continuous outcomes.
	Secondary outcomes : Descriptive statistics, Kaplan Meier analysis, Poisson regression and linear mixed modeling and will be used as appropriate.

SCHEMATIC OF THE STUDY DESIGN

Enrolment and consent: Once informed consent is obtained, the Dialysis Symptom Index (DSI) will be administered to all participants. Those who score 0 on the DSI (no symptoms) will be deemed ineligible for the study

Randomization: To avoid bias, randomization will be performed following the baseline assessment.

Intervention phase: Participants in "intervention" group will receive study intervention during this time.

2.1 Background information

Individuals with end-stage kidney disease (ESKD) require renal replacement therapy such as hemodialysis (HD), peritoneal dialysis, or renal transplantation to sustain life. In Canada, the majority (76%) of the 5500 individuals who enter this stage of kidney disease annually start in-centre HD.¹ Individuals on HD are known to have low self-reported functional status, and poor health-related quality of life (HRQOL) when compared to general population controls.^{2, 3} Functional status is an important component of HRQOL and refers to the ability to perform activities required for daily life.

Symptom burden, the combined impact of the number and severity of symptoms experienced by an individual, is high in HD and contributes to poor functional status and HRQOL. Cross-sectional studies show that 30-80% of individuals on HD have at least one symptom that is related to ESKD or dialysis treatment, with a mean of 6-20 symptoms endorsed per individual.⁴⁻⁸ In a systematic review of symptom burden in chronic kidney disease (CKD), fatigue was identified as the most widespread symptom, with a weighted mean prevalence of 81%.⁵ Frequent symptoms (>50% prevalence) also included lack of sleep, pain, muscle cramping, pruritus (itch), decreased appetite, drowsiness and dry skin.⁵, Other symptoms identified in more than 30% of patients include restless legs syndrome, difficulty concentrating, anxiety and depression.^{4, 5, 10}

Increased physical activity through exercise programming may play a role in symptom control. Increased prevalence of symptoms is correlated with low physical activity in individuals on dialysis. ^{11, 12} Even in low functioning HD patients, exercise programming has been shown to be safe and to improve outcomes closely associated with symptom burden, such as functional status and HRQOL. ^{13, 14} As well, several small randomized controlled trials (RCTs) have demonstrated improvement in specific individual HD-related symptoms such as restless legs and insomnia. ¹⁵⁻²⁵ Using RCT methodology, we aim to characterize the role of exercise rehabilitation in managing symptom burden in chronic HD to determine if such a program can ameliorate common symptoms like insomnia, pain and fatigue, resulting in improved quality of life and reduced disability over the long term.

2.1.1 HD-related symptoms are a research priority

Multiple studies have shown that symptom burden in individuals on HD is similar to those living with metastatic cancer. HD therapy itself does little to improve symptom burden and may worsen symptoms. In a study of 698 hemodialysis patients followed for 1 year after starting HD, symptoms worsened in 23%, did not change in 56% and improved in only 19% of patients over the first year on HD. Furthermore, healthcare providers have limited awareness of the presence and severity of symptoms in patients on HD. When responses to the Dialysis Symptom Index (DSI) were compared between 75 HD patients and 18 providers (nephrologists, nurse practitioners, physician assistants and nurse managers), providers underreported 97% of symptoms and underestimated symptom severity in 63%. Even when recognized, limited effective treatments exist for most symptoms. For those few

symptoms for which there are effective pharmacological therapies (uremic pruritus, restless legs syndrome, and depression), patients may be hesitant to take additional medications due to pre-existing medication burden (median of 19 medications per day) or attribution of symptoms to acute events.²⁷⁻²⁹

Most importantly, the identification of effective treatments for HD-related symptoms has been identified as an important knowledge gap for HD patients and their caregivers. Using methodology established by the James Lind Alliance, patients, caregivers and healthcare providers from across Canada identified the improvement of symptom burden and quality of life as research priorities for individuals at or nearing dialysis.³⁰ Using similar methodology, international groups have identified fatigue/energy, sleep, anxiety/stress and decreased appetite as key outcomes to be assessed in any future research studies.^{31, 32}

2.1.2 Exercise programming may play a role in symptom control

Low physical activity is correlated with increased prevalence of symptoms in individuals on dialysis. ^{11, 12} In an observational study of 1643 incident dialysis patients, each 10-point increase in self-reported physical activity level measured using the Human Activity Profile was associated with a 20% decrease in symptoms of insomnia and restless legs and a 37% decrease in symptoms of depression. ¹²

Evidence from small RCTs suggests that exercise can improve specific HD-related symptoms. In two RCTs with a combined total of 48 patients, cycling during HD for 30 minutes, 3x/week for 16 and 26 weeks led to a significant decrease in International Restless Leg Scale score as compared to no intradialytic exercise. 15, 16 Similarly, a single RCT with 28 male participants showed significant improvement in Pittsburgh Sleep Quality Index score after 3 weeks of intradialytic cycling (5.85; SD 2.61) as compared with the control group (-1.00; SD -1.00). 18 However, another study with 22 participants showed no significant difference between exercise and control groups in change in sleep quality measured by sleep diary after 26 weeks. 15 Hadian et al. demonstrated that 83% of participants who exercised (walking for 20 minutes, thrice weekly for 8 weeks) had decreased cramping as compared with 31% of participants in the control group (p=0.014). Finally, using the Beck Depression Inventory and various exercise regimens (intradialytic cycling, walking or jogging outside of dialysis) for between 10 weeks to 1 year duration, several small RCTs have observed a 35-40% reduction in depressive symptomatology in exercisers as compared with non- exercise controls. 20-24 The effect of exercise on mood has been more variable in studies that used other self-reported tools to measure symptoms of anxiety and depression.^{20, 23,} 24,25

Although the signal provided by these small heterogeneous studies is promising, the impact of exercise on several common HD-related symptoms (nausea, extremity pain, dyspnea) is unknown and no study has examined the effects of exercise on overall symptom burden in HD. The opportunity to reduce symptom burden, address a knowledge gap important to patients and potentially improve functional status and HRQOL using an accessible, non-pharmacologic intervention underscores the importance of further research into the effects of exercise on symptom burden in ESKD.

2.1.3 Reduced symptom burden may be a major driver of improved HRQOL in ESKD

Not surprisingly, increased symptom burden is strongly associated with poor HRQOL and low functional status in individuals on HD. In 120 individuals within 3 months of commencing HD, greater symptom burden was associated with lower HRQOL as measured by the physical and mental components scores of the Short Form 36 (SF-36). Using the DSI, Weisbord et al demonstrated that the burden of mental and physical symptoms in HD patients were independently associated with poor HRQOL measured using the Illness Effects Questionnaire (r=0.6 and 0.61, respectively). Finally, in a cohort of 301 Chinese HD patients with heavy symptom burden as measured by DSI, symptom burden was strongly correlated with reduced HRQOL as measured using the SF-36 (rs = -0.619; p<0.001).

Several recent systematic reviews of exercise programming in HD have demonstrated improvement in HRQOL as measured by generic self-reported instruments.^{14, 34} It is plausible that improved symptom control is a major driver of the improvement seen in HRQOL after exercise participation in this population. However, only a single study has investigated the effect of exercise on dialysis-related symptom burden using a questionnaire with limited previous validation and showed no benefit.²⁵ Using validated measurement tools for symptom burden and HRQOL with extensive previous use (DSI and EuroQol-5D3L respectively), we hope to further characterize the role of symptom burden in the improvements to HRQOL seen with exercise in the HD population.

2.1.4 Reduced symptom burden through exercise may decrease adverse outcomes

Dialysis confers an elevated risk of morbidity, which is further magnified in individuals with low physical function and physical activity levels.³⁵ Prospective observational studies in both incident and prevalent HD patients have found that individuals who are less active have a 30% higher mortality risk than individuals who are more active, even when adjusted for multiple confounders including age, sex, race, albumin, comorbidities, smoking and socioeconomic status.^{36, 37} This association was linear at all levels of activity, suggesting that even low functioning individuals on dialysis would benefit from becoming as active as possible.³⁷ Similarly, multiple observational studies have also shown that frail status and/or low self-reported physical function are associated with a 15-50% increase in falls, institutionalization and hospitalization rates among hemodialysis patients.³⁸⁻⁴³

Symptom burden also plays a role in the high rates of morbidity and mortality seen in the HD population.^{38, 44} In a large international observational study using DOPPS data that demonstrated a 25% increased risk of hospitalization and mortality with each 10 point decline in HRQOL, symptoms alone (measured by the Kidney Disease Component Summary), increased the risk of mortality and hospitalization by 8% when adjusted for albumin, comorbidities and other variables known to be associated with adverse outcomes.³⁹ In addition, restless legs, worsening insomnia and symptoms of depression have all been associated with a 30-40% increase in all-cause mortality risk in incident HD patients when adjusted for age, race, and comorbidities.^{17, 45, 46} Similarly, depressive symptoms have also been associated with increased risk of hospitalization in incident HD patients.

Observational data suggest a link between low physical activity, low physical function, HD-related symptoms, poor HRQOL and increased hospitalization and mortality risks. No interventional trial has investigated the role of exercise programming on long-term outcomes. Our knowledge translation plan (Appendix 4) includes leveraging the methodology already in place for our study to gather the information required to design and implement a multicenter trial looking at the effect of exercise rehabilitation on long-term clinical outcomes, including frailty, hospitalization and mortality in HD.

2.2 Significance and rationale

Individuals on HD have high symptom burden, low functional status and poor HRQOL, for which effective treatments known to impact clinical outcomes are extremely limited. The identification of effective treatments for dialysis-related symptoms has been identified as a research priority by HD patients, their caregivers and healthcare providers in Canada.³⁰

In other chronic disease programs, exercise rehabilitation programs, incorporating resistance and aerobic exercise and lifestyle education, have demonstrated benefits to outcomes closely associated with symptom burden such as physical function, and HRQOL.^{47, 48} Although the immediate post-program benefits of such organized programs have been demonstrated for physical function and HRQOL outcomes in the ESKD population,^{21, 49, 50} the effect of exercise rehabilitation on symptom burden in HD patients is unknown.

We hypothesize that an exercise rehabilitation intervention will decrease symptom burden resulting in improved HRQOL and clinical outcomes such as functional status and frailty. Such results would have significant implications for individual Canadians with kidney disease, their caregivers and the healthcare system overall.

2.3 Potential Risks and Benefits

2.3.1 Known Potential Risks

The risks associated with study participation will be fully disclosed to participants. Occurrence of events will be monitored at every study visit, and will constitute grounds for termination of study intervention in study patients – these participants will remain in the study on a strictly observational basis.

Risk of Disclosure of Personal Health Information: There is a potential risk of disclosure of personal health information with any clinical study and database. All study personnel have undergone ethics, GCP CITI training, and taken a Pledge of Confidentiality (PHIA).

A secure study database will be maintained for the trial purposes. The study database will utilize appropriate security measures to protect patient privacy and data. All study participant information will be entered using a unique study identifier. All data and samples will be analyzed using the study identifier with no personal health information linked to it. Each Site Principal Investigator will hold the key to the de-identified information in a locked and secure office. The Subject Identification Code List that links the identity of the participant with subject ID for de-identified data will be maintained with the trial's master file, according to ICH-GCP, Section 8.3.

Risk of Exercise: Participation in this trial of monitored exercise is low risk. Multiple previous studies of intradialytic exercise in individuals with ESKD have demonstrated no significant adverse events with such interventions. However, it should be noted that none of these studies were powered for safety outcomes. Participants will be carefully pre-screened for safety to exercise by the attending HD unit nephrologists and study staff and the program of exercise will be modified for each individual's personal health status and gradually incremental in intensity and duration. However, there is a certain degree of risk involved in the initiation of any exercise program. Patients will be monitored for the following risks:

- Muscle or joint soreness following initiation of an exercise program
- Low blood pressure on hemodialysis after exercising
- Develop chest pain (angina) during or after exercise
- Develop an irregular/fast heart rhythm (arrhythmia) during or after exercise
- Develop an acute coronary syndrome during or after exercise
- Develop hypoglycemia during or after exercise in setting of diabetes on medications
- Develop tendon rupture during or following exercise
- There is a very small risk of death related to the above side effects if they occur

2.3.2 Known Potential Benefits

The identification of effective treatments for dialysis-related symptoms has been identified as a research priority by HD patients, their caregivers and healthcare providers in Canada. In other chronic disease programs, exercise rehabilitation programs, incorporating resistance and aerobic exercise and lifestyle education, have demonstrated benefits to outcomes closely associated with symptom burden such as physical function, and HRQOL.^{47, 48} Although the immediate post-program benefits of such organized programs have been demonstrated for physical function and HRQOL outcomes in the ESKD population, ^{21, 49, 50} the effect of exercise rehabilitation on symptom burden in HD patients is unknown.

Decreased symptom burden through exercise programming and the resulting improvements in HRQOL and clinical outcomes such as functional status and frailty would have significant implications for individual Canadians with kidney disease, their caregivers and the healthcare system overall.

3 OBJECTIVES AND PURPOSE

The **primary objective** of this study is to determine the effect of a 12-week exercise rehabilitation program consisting of structure lifestyle education, resistance exercise and intradialytic cycling on symptom burden at 12, 26 and 52 weeks in adult individuals on chronic hemodialysis.

Our **primary hypothesis** is that a participation in 12-week exercise rehabilitation program will decrease symptom burden immediately after the program at 12, 26 and 52 weeks in individuals on chronic hemodialysis.

Our secondary objectives include:

- 1. To determine the effect of a 12-week exercise rehabilitation program on health-related quality of life at 12, 26, and 52 weeks.
- 2. To determine the effect of a 12-week exercise program on:
 - a. Time required for recovery post hemodialysis
 - b. Physical activity behavior at 12, 26, and 52 weeks
 - c. Exercise endurance/capacity at 12, 26 and 52 weeks
 - d. Frailty status at 12, 26, and 52 weeks
 - e. Self-efficacy to exercise at 12, 26, and 52 weeks
 - f. Hospitalization rate over 1 year and hospital length of stay
 - g. Mortality at 1 year

4 STUDY DESIGN AND ENDPOINTS

4.1 Description of the Study Design

This is a Phase 4 single-center prospective randomized controlled trial of prevalent adult chronic HD patients. Patients will be screened for eligibility **and one hundred and fifty patients** with dialysis-related symptoms as confirmed by baseline DSI symptom burden score > 0 will undergo 1:1 randomization to the two-step intervention (intensive and maintenance phase) and control arms for 1 year. The total study duration is approximately 4 years.

Please see the Schematic of the Study Design, p. 8.

4.1.1 Study Timeline

	Year	Year 1			Year 2 Year 3			. 3	3			Year 4				
	Q1	Q2	Q3	Q4	Q1	Q2	Q3	Q4	Q1	Q2	Q3	Q4	Q1	Q2	Q3	Q4
Patient Recruitment																
Ongoing Follow-up																
Statistical Analyses																
Knowledge Translation																

4.2 Study Outcomes

4.2.1 Primary Outcomes

Change in symptom burden from baseline to 12weeks as measured by the Dialysis Symptom Index (DSI) Severity Score (Appendix B-1). This will be measured as the proportion of individuals who have a decline of 7 points or more in symptom burden as defined by DSI symptom severity score from baseline to 12weeks. The DSI is a 30-item self-administered questionnaire with low administrative burden developed to measure the presence (yes/no) and severity ("how much did it bother you" by 5 point Likert-scale ranging from "not at all" to "very much") of common emotional and physical symptoms over the previous week in individuals receiving maintenance HD.⁵¹ Symptom severity scores can range from 0 to 150. A 7-point change in severity score is likely to be clinically significant because this magnitude of change is: a) consistent with the resolution/addition of 1 "very bothersome" symptom plus a 1 point change in severity of 2 symptoms and likely to be significant to patients; and b) is approximately 1 standard error of the mean based on our pilot data (SD 30, n=18) and consistent with distribution-based methods. The DSI has been shown to be reliable in predicting HRQOL in multiple studies in North American and European HD populations.^{6,51}-

Change in symptom burden from baseline to 12weeks as measured by modified DSI Severity Score. Based on our experience and evidence from small clinical trials, we anticipate that the maximum benefit from exercise will occur in a subset of symptoms on the DSI. These include: a) muscle cramps; b) restless legs; c) feeling tired or lack of energy; d) difficulty concentrating; e) worrying; f) feeling nervous; g) trouble falling asleep; h) feeling irritable; i) feeling sad; j) feeling anxious. Thus, we will perform a subgroup analysis of DSI severity scores for the 11 symptoms listed above. This pragmatic approach will lead to less participant burn out than if individual measures were used for each symptom.

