7.3.2 Randomization and Blinding

Participants will be randomly assigned to the Intervention Arm or Control Arm. Randomization will be performed by a third party using *block randomization* with randomly permuted block sizes with an overall 1:1 allocation. To ensure *allocation concealment* and *to minimize bias*, the randomization code will not be released until baseline testing is completed. After randomization has occurred, the site's research staff will be responsible for ensuring the assigned randomization number is applied to all study documents for each participant. Due to the nature of the intervention in this trial, randomization to the Intervention Arm cannot be blinded to the site PI's or participants. However outcome assessors and study statistician will be blinded to study group during analysis (Prospective Randomized Open Blinded-Endpoint study).

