7.4 Study Groups

7.4.1 Control Arm, Standard-of-care

As recommended in clinical practice guidelines for individuals with CKD, participants will receive standardized exercise counseling at baseline.^{76, 77} Although not prohibited from participating in exercise outside of the study protocol, participants in the control group will not undergo a formal structured exercise intervention and will be asked to refrain from intradialytic cycling during the 12-week intervention period. Exercise activity will be tracked via weekly self-reported log sheets. The study kinesiologist (to control for personal trainer effect) will collect log sheets weekly during the study period. Outcome measurements will occur according to the Schedule of Events (Section 7.5).

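### The blinded-endpoint label does not fit the primary and principal secondary outcomes, which are rated after randomization by participants who know their arm

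*Combined protocol and SAP*

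**What the plan says.** On blinding, section 7.3.2 first concedes that "randomization to the Intervention Arm cannot be blinded to the site PI's or participants". The next sentence reads: "However outcome assessors and study statistician will be blinded to study group during analysis (Prospective Randomized Open Blinded-Endpoint study". The Design row of the synopsis describes the trial as having "allocation concealment and assessor blinding".

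On the primary outcome, section 4.2.1 states: "The DSI is a 30-item self-administered questionnaire with low administrative burden". The form in Appendix 3.1 asks participants whether they had each symptom in the past week and how much it bothered them. Section 4.2.2 describes the principal secondary outcome, EQ-5D-5L with the VAS, as self-administered too.

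Three features bear on how much protection exists:

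- Baseline is measured before allocation is known, because "the randomization code will not be released until baseline testing is completed" (7.3.2).
- The comparator is open standard care with counseling: "participants in the control group will not undergo a formal structured exercise intervention" (7.4.1).
- The study kinesiologist collects control participants' logs weekly, with the stated purpose of controlling for a personal trainer effect (7.4.1).

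**The concern.** An open design with blinded endpoint assessment protects an outcome when someone who does not know the allocation makes the judgement. For the DSI the participant makes the judgement, and the participant knows the allocation. A blinded staff member who hands over the form, or reads it out, does not change who is rating. The design therefore states a property that its primary and principal secondary outcomes lack.

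This matters for interpretation. The exercise arm receives one-on-one education, close supervision of the first cycling sessions and at least weekly check-ins (7.4.2). The DSI includes items open to expectation, such as worrying, sadness, irritability and tiredness. A modest tendency to report improvement would look like a treatment effect. A reader who takes the label at face value could give that explanation too little weight.

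**Working it through.** **Step 1. Who makes each 12-week rating.**

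| Outcome | Section | Rater | Can assessor blinding cover the rating? |
|---|---|---|---|
| DSI (primary) | 4.2.1, App. 3.1 | Participant | No |
| EQ-5D-5L and VAS (principal secondary) | 4.2.2, App. 3.2 | Participant | No |
| Recovery time | 4.2.3 item 1 | Participant | No |
| Godin score | 4.2.3 item 3b, App. 3.3 | Participant | No |
| Self-efficacy | 4.2.3 item 6, App. 3.6 | Participant | No |
| Frailty: exhaustion item | App. 3.5 | Participant | No |
| Frailty: grip, timed walk | App. 3.5 | Staff-measured | Yes |
| Shuttle walk | 4.2.3 item 4 | Staff-measured | Yes |

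The label fits the last two rows. It does not fit the outcomes on which the trial's main conclusions rest.

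**Step 2. The plan's own sample size.** Inputs from 9.2: 50% versus 25% responders, alpha 0.05, power 0.80, taken as two-sided. With mean proportion 0.375 and pooled variance:

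n = [1.960 × √(2 × 0.375 × 0.625) + 0.842 × √(0.25 + 0.1875)]² / 0.25² = 57.7, so 58 per arm. This reproduces the stated figure.

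At the stated 30% dropout, 75 × 0.70 = 52.5, so about 52 evaluable per arm. The range 52 to 58 is used below.

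**Step 3. Illustration of sensitivity.** The documents give no size for reporting bias, so the shift is an assumption.

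- No true effect; 25% control responders (9.2).
- Normal DSI change with SD 16 (9.2), or SD 30. The 30 is the pilot SD in 4.2.1; the text does not say that it is the SD of change.
- Assumed shift b of 3 or 5 points in the exercise arm only.

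Responder rate in exercisers: p = Φ(Φ⁻¹(0.25) + b/SD), with Φ⁻¹(0.25) = −0.674.

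- SD 16, b = 3: Φ(−0.674 + 0.1875) = 0.313
- SD 16, b = 5: Φ(−0.674 + 0.3125) = 0.359
- SD 30, b = 3: Φ(−0.674 + 0.100) = 0.283
- SD 30, b = 5: Φ(−0.674 + 0.1667) = 0.306

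Rejection probability = Φ((d − z·s₀)/s₁) + Φ((−d − z·s₀)/s₁), where d = p − 0.25, s₀ is the pooled standard error and s₁ the unpooled one. For SD 16, b = 3, n = 52: d = 0.063, s₀ = 0.0882, s₁ = 0.0880, giving 0.110.

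| SD | Shift | alpha 0.05, n = 52 / 58 | alpha 0.01, n = 52 / 58 |
|---|---|---|---|
| 16 | 3 | 11.0% / 11.7% | 3.2% / 3.5% |
| 16 | 5 | 22.4% / 24.5% | 8.4% / 9.5% |
| 30 | 3 | 6.6% / 6.8% | 1.6% / 1.6% |
| 30 | 5 | 9.7% / 10.2% | 2.7% / 2.9% |

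The 0.01 column is shown because 9.3.3 sets that threshold for all analyses, whereas 9.2 designs at 0.05.

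The mean-change comparison, also planned in 9.3.1, is more exposed. With SD 16 and alpha 0.05 it rejects in about 16 to 17% of trials for 3 points and 36 to 39% for 5 points.

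**The case against.** The strongest reply is that nothing is hidden. The statement that participants cannot be blinded comes directly before the label, the label itself contains the word Open, and 4.2.1 calls the DSI self-administered. An exercise program cannot be masked, so open symptom reporting comes with the research question. All of this stands. The fault lies in the label and in how the result will be worded, not in concealment or in the choice of outcome.

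A reader might go further and infer that the DSI has no protection at all. The documents do not support that. The baseline score is taken before the code is released, the blinded statistician protects analysis choices, and weekly kinesiologist contact in controls partly evens out attention. What is missing is blinding of the post-randomization rating.

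A reader might also infer that the DSI items outside the modified DSI could expose reporting bias, so that a similar improvement there would be a warning sign. The documents do not support that either:

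- Section 4.2.1 says only that "we anticipate that the maximum benefit from exercise will occur in a subset of symptoms on the DSI", which does not predict zero benefit elsewhere.
- Section 2.1.2 says the effect on nausea, extremity pain and dyspnea is unknown.
- The remaining items include trouble staying asleep and bone or joint pain, which might truly improve.
- They also include muscle soreness, a listed exercise risk (2.3.1), which might truly worsen.
- The subset is not fixed: 4.2.1 refers to 11 symptoms but lists ten.

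A real general benefit would then have to be reported as bias. Those items are not valid negative controls.

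Nor is the plan without less subjective outcomes. The shuttle walk, accelerometry, hospitalization and mortality are all collected, although no section ties them to the DSI result. Under the COVID-19 procedure (Appendix 5), accelerometry and the physical tests are not done at affected visits.

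**Conclusion.** The point holds as a mismatch between the stated design and the outcomes it is meant to describe. The 12-week DSI, the EQ-5D-5L and VAS, recovery time, Godin score, self-efficacy and the exhaustion item are open-label participant reports. Neither assessor blinding nor statistician blinding alters that.

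The table in the working shows only how sensitive the responder test would be to a shift of a given size. Its figures depend on an assumed 3- to 5-point shift, a normal distribution of change, a 25% control rate and the SD chosen. They fall by more than half when the 0.01 threshold is used. It would be wrong to read them as the false-positive rate of this trial, because the size and even the presence of reporting bias are unknown from the documents.

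**What to change.** 1. In 7.3.2 and the Design row of the synopsis, drop the blinded-endpoint label for the self-reported outcomes. State instead that outcome-assessor blinding protects the staff-measured performance tests (shuttle walk, grip strength, timed walk); that the statistician is blinded; and that the DSI, EQ-5D-5L and VAS and the other questionnaires are open-label participant reports.
2. In 9.3.1, or wherever the conclusion is framed, word the primary result as an effect on unblinded, self-reported symptom burden. Mention the protections that do exist: baseline testing before allocation and weekly kinesiologist contact in controls.
3. Do not add a rule that treats improvement in DSI items outside the modified DSI as a sign of reporting bias.

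The cost is a few sentences. No new data, visits, participants or analyses are needed. The stated design becomes slightly less favourable, but accurate.
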